#### 49 **Group 1: Standard of care group:**

Dyads randomized to the control group will be discharged per local hospital policy with instructions from their team. They will be given the contact number of the study team to call as needed and will then be seen at day 30 of an in-person visit. We will follow the medical record of the patients to evaluate for intervening readmissions but will not call them specifically. The standard of care of these patients is usually either follow-up as needed or occasional phone calls as needed by the clinical team. The standard of care also depends on the acuity of the presentation and the ability of the patient to follow-up. For this study, we will require a 30-day visit from the patient and caregiver.

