**41. \* Provide justification for the sample size:**

42 Sample size: Prior studies and our cohort have shown a 30-day readmission rate around 33% using current practice, and of which 20% were  
43 considered avoidable. Per our preliminary data, the rate of 30-day avoidable readmission reduced to 5%. However, we will be circumspect  
44 and increase this relative avoidable readmission rate to 9%. In order to determine a similar reduction at 80% power at an  $\alpha = 0.05$  level of  
45 significance we would require 45 patients in the Health-IT+scheduled visits, 45 patients in the Health- IT only and 45 patients in the standard  
46 of care group per site leading to a total of 135 patients per site or 405 total patients. This will also include 405 caregivers. Allowing for a 10%  
47 dropout rate, we plan to we will enroll a total of 450 patients, of which 150 will be randomized to health-IT+scheduled visits, 150 to health-IT  
48 only and 150 to standard of care across all three sites. This will be accompanied by an equal number of the respective caregivers bringing the  
49 grand total of subjects across all three sites to 900.

50 Therefore at McGuire VAMC we will enroll 50 patients and 50 caregivers in each group for a total of 300 subjects (150 patients and  
50 caregivers).

51

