## 2 Compensation

3  
4 1. If the patients and caregiver dyad completes the study 30-day follow-up (or are hospitalized in between, which will end their study participation),  
5 we will provide them a check for \$100 for the patient and \$75 for the companion for a total of \$175 for the study participation.  
6

7 2. **If compensation will be pro-rated, explain the payment schedule:** No pro-  
8 rated compensation will be provided.  
9

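### The 10% dropout is met only by extra enrolment: no step obtains the 30-day readmission outcome of dyads that stop early, and record follow-up independent of contact is written only for Group 1

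*Combined protocol and SAP*

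**What the plan says.** The sample-size justification (Study Population) sets 45 patients per arm per site, "of care group per site leading to a total of 135 patients per site or 405 total patients". It then allows for 10% dropout: "dropout rate, we plan to we will enroll a total of 450 patients", 150 per arm. It does not define a dropout. The document gives no analysis set and no rule for a missing outcome.

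The section on deciding avoidable readmissions has a three-hepatologist committee, not told the assignment, classify each readmission from its discharge summary. Summaries of all patients admitted within 30 days go to the committee.

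The text on finding readmissions differs by arm:

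- **Group 1:** "We will follow the medical record of the patients to evaluate for intervening readmissions but will not call them specifically".
- **Groups 2 and 3:** daily app contact, and outreach when nothing has been entered for more than 24 hours. Once a patient is readmitted, the team contacts the caregiver, recovers the phones and requests the summary from an outside hospital. Group 3 adds two calls and a day-15 visit.
- **All groups:** a day-30 visit.

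Under Compensation, the dyad is paid without pro-rating on this condition: "If the patients and caregiver dyad completes the study 30-day follow-up (or are hospitalized in between, which will end their study participation"). Amendment 2 moves to 1:1 randomisation with 232 patients and restates no dropout rate.

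**The concern.** Stopping the app and losing the outcome are different events, and the plan does not separate them. A patient who returns the phone, loses the caregiver or misses day 30 can still be readmitted, and that readmission still produces a discharge summary. Enrolling extra patients replaces the lost numbers but not the lost outcomes.

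Two things are at stake. The first is bias. Only the health-IT arms carry daily entries by two people and weekly cognitive testing run by the caregiver. The background section says these patients may have impaired judgment and memory, and the risk section names encephalopathy as a major reason for admission. Deterioration could plausibly cause both stopping and readmission. If the written procedures are followed literally, a Group 1 leaver's record is still checked, while a Group 2 or 3 leaver has no equivalent written step. The second is power: outcomes that could have been obtained are given up.

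**Working it through.** **Inputs.** From the sample-size section: 405 patients (135 per arm), 10% dropout, 450 enrolled (150 per arm), 80% power, alpha 0.05. The rates are ambiguous. The text reads "Sample size: Prior studies and our cohort have shown a 30-day readmission rate around 33% using current practice, and of which 20% were" avoidable, with 9% assumed under health-IT. The test and its sidedness are not stated.

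**1. The plan's enrolment figure.** 405/(1 − 0.10) = 450 and 135/(1 − 0.10) = 150. Both match exactly. Implied dropouts: 450 − 405 = 45, or 15 per arm.

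**2. Which rates lie behind 135 per arm.** Take 20%/9%/9% as absolute rates in a three-arm chi-square test (2 df).

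- Mean rate = (0.20 + 0.09 + 0.09)/3 = 0.1267.
- Noncentrality per patient per arm = [(0.0733)² + 2 × (0.0367)²]/(0.1267 × 0.8733) = 0.0729.
- 80% power needs 133 per arm, against 135 stated. Power is 80.9% at 135.

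A pairwise two-sided test of 20% against 9% needs 160 per arm. The literal reading (20% of 33% = 6.6%; 9% of 33% = 2.97%) needs 440 per arm with the three-arm test. So 20%/9%/9% is used below, as the reading that comes closest.

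**3. Expected avoidable readmissions against dropouts (135 completers per arm).**

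| | Events | Dropouts |
|---|---|---|
| Control | 0.20 × 135 = 27.0 | 15 |
| Each health-IT arm | 0.09 × 135 = 12.15 | 15 |
| Total | 27.0 + 2 × 12.15 = 51.3 | 45 |

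The expected difference between control and one health-IT arm is 27.0 − 12.15 = 14.85 events, about the 15 dropouts per arm.

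**4. What the missing outcomes could do.** Let dropouts have risk *c* in control and *t* in a health-IT arm. Over all 150 per arm:

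difference = (27 + 15c)/150 − (12.15 + 15t)/150 = 9.9 points + 10 points × (c − t)

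Among completers alone the difference is 20 − 9 = 11 points.

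| Assumed dropout risk | Control | Health-IT | Difference (points) |
|---|---|---|---|
| 40% in both | 33/150 = 22.0% | 18.15/150 = 12.1% | 9.9 |
| 20% control, 40% health-IT | 30/150 = 20.0% | 18.15/150 = 12.1% | 7.9 |
| 40% control, 20% health-IT | 33/150 = 22.0% | 15.15/150 = 10.1% | 11.9 |
| 0% control, 100% health-IT (bound) | 27/150 = 18.0% | 27.15/150 = 18.1% | −0.1 |
| 100% control, 0% health-IT (bound) | 42/150 = 28.0% | 12.15/150 = 8.1% | 19.9 |

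The dropout risks are assumptions; the documents give none.

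**5. Power if all outcomes are kept (150 per arm).** Three-arm: 80.9% rises to 85.1%. Pairwise two-sided: 73.0% rises to 77.5%.

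**6. Sensitivity to the literal reading.** Expected events are 0.066 × 135 = 8.9 in control and 0.0297 × 135 = 4.0 in each health-IT arm. The difference of 4.9 is about a third of the 15 dropouts per arm, so missing outcomes would weigh more heavily.

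**The case against.** Inflating for dropout is routine, and the arithmetic is right. It sets a sample size and defines no analysis set. With no definition given, dropout might already mean only patients whose outcome cannot be obtained. Consent pages are not in the reviewed text, so wording there on data use after withdrawal cannot be presumed absent. This stands: exclusion of dropouts is an inference.

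Capture in Groups 2 and 3 is also better than a quick reading suggests. The committee is to receive summaries for all patients admitted within 30 days, without limit by arm. Outside summaries are requested, silence in the app prompts outreach, and a 30-day visit is standard care for everyone. This stands in part. Those steps help while a dyad is in contact or once a readmission is known; none looks for a readmission in a dyad that has left.

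Nor does a record check capture everything. Local records can miss admissions elsewhere, which is why the fix includes a call.

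Three stronger readings are tempting, and the documents do not support them:

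- **That dropouts outnumber events.** This is true only within each health-IT arm (12 against 15). It is false for control (27 against 15) and in total (51 against 45).
- **That the loss favours health-IT.** The mechanism is plausible, but no figure shows it. Groups 2 and 3 are contacted daily and Group 1 is not called, so loss could be greater in control. Equal dropout risk moves the difference only from 11 to 9.9 points.
- **That the payment rule drives uneven loss.** It is the same in every arm and also pays dyads whose patient is readmitted.

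**Conclusion.** The point holds as a gap in outcome ascertainment. The plan meets an expected 45 early leavers by extra enrolment alone, has no step that obtains their outcome, and writes contact-independent record follow-up for one arm only, although the endpoint rests on documents that exist whether or not the dyad stays engaged.

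The number of missing outcomes per arm (15) about equals the expected event difference (14.85), so the result is exposed to how those patients fared. At the extremes the effect disappears or nearly doubles. Under the moderate assumptions shown, the difference runs from 7.9 to 11.9 points. The direction is unknown.

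These sizes rest on the 20%/9%/9% reading, on 15 dropouts in each arm, and on dropouts having no recorded outcome, which is inferred. They apply to the three-arm design. After Amendment 2 the gap remains, but the final split is not given: earlier patients were randomised 1:1:1 and later ones 1:1. No per-arm figure can be derived.

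**What to change.** Add one protocol paragraph separating stopping the app from leaving the trial, worded identically for every arm:

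- Review the medical record to day 30 for every randomised patient, whatever the app use, phone return, caregiver status or day-30 attendance.
- Make one closing call after day 30 to the patient or caregiver to ask about admissions elsewhere. Because it falls after the outcome window, it does not alter Group 1's standard of care.
- Send any resulting discharge summary to the blinded committee.
- Analyse all randomised patients in their assigned arm. Treat the outcome as missing only where consent to record use is withdrawn or the outcome cannot be obtained, and report those numbers by arm.

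Leave the 10% allowance as it is; the documents give no basis for assigning it to consent withdrawals alone.

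The cost is a chart check and a short call per early leaver: about 45 dyads in the three-arm design, or about 23 after Amendment 2 if 10% still applies (0.10 × 232 = 23.2). The downside is that the estimate will include non-users and may be slightly less favourable to the app.

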**52. \* List the study inclusion criteria:**

53 Cirrhosis patients  $\geq 21$  years of age hospitalized for non-elective reasons

54 • Adult caregiver and the patient living in the same house

55 • Both (caregiver and patient) should be able to complete the Patient Buddy training and evaluation

56 • Discharged home from the hospital

57 •

**58. \* List the study exclusion criteria:**

59 • Elective hospitalization

60 • Lack of an adult caregiver

- 1   •   Active alcohol/substance abuse within 1 month of the hospitalization
- 2   •   Unable to perform training or give consent
- 3   •   Patients discharged to hospice, nursing home or extended care facilities
- 4   Patients on Hemodialysis
- 5   pregnant women
- 6   patients with limited English proficiency

## 7 Potential Subject Identification and Recruitment

8

9

10 There will not be any special recruitment flyers since all patients will be hospitalized at VA and will be enrolled through direct contact after  
11 referral or by reviewing the inpatient lists for potentially eligible patients.

12 Subjects will be recruited from the Inpatient Service at VAMC. Each morning, the CITI-trained nurse coordinator (who will also act as the  
13 nurse coordinator) will check with the inpatient attending if cirrhotic subjects have been admitted. These subjects will be reviewed by the PI  
14 and/or co-investigators. If they appear to be reasonable candidates, the coordinator and investigators will discuss the study with them and  
15 their caregivers. Sufficient opportunity will be provided to them to have all their questions/concerns answered before consent will be obtained.

16 If subjects and caregivers are agreeable, study activities will start at the day of discharge

17

## 18 Privacy

19

20 Before approaching the patients and caregivers, the study team member will make sure that the conversation cannot be overheard and will  
21 get a private setting in the inpatient unit. This maintenance of privacy will continue throughout the process of study conduct and data  
22 dissemination and during the contact between study participants and the team during the 30-day follow-up period.

23 **Costs to Participants:** no specific study related costs to the patients or caregivers.

24 All medical care provided for the study participant will not be study related, but standard of care.

25 The medical team following the study subject as a patient in clinic at week 2 (group 3) and day 30 (all groups) may perform the following  
26 procedures as standard of care: vital signs to include BP, HR, Temperature, height, and weight. The medical team may also send the following  
27 labs as standard of care: CBC with diff, comprehensive metabolic panel, liver panel and pt/inr. All of these procedures will not be covered by  
28 the study and will be charged to the patient's insurance company. Since the medical procedures needed for pt care will be as standard of care,  
29 the current process of determining medical coverage

30

31

32

33

34

35

36

37

38

39

40

41

42

43

44

45

46

47

48

49

50

51

52

53

54

55

56

57

58

59

60

1 will be used.

## 2 Compensation

3  
4 1. If the patients and caregiver dyad completes the study 30-day follow-up (or are hospitalized in between, which will end their study participation),  
5 we will provide them a check for \$100 for the patient and \$75 for the companion for a total of \$175 for the study participation.  
6

7 2. **If compensation will be pro-rated, explain the payment schedule:** No pro-  
8 rated compensation will be provided.  
9

## 10 Risks, Discomforts, Potential Harms and Benefits

11 13. \* **Describe the risks of each research procedure to participants or others.**

14 1. Physical risks: none from the use of the app.  
15

16 2. Psychological/social risks: Very small risk of loss of confidentiality and privacy. They may feel anxious about completing the  
17 cognitive tests especially if they notice a decline.

18 3. Financial risks: since groups 2 and 3 will be in greater contact with their care team, they may be referred to  
19 their medical team for treatment or medication changes (for example), which may result in unanticipated costs for the  
20 participant.

21 2. \* **Describe how the risks / harms will be minimized:**  
22

23  
24 1. Psychological/social risks: Very small risk of loss of confidentiality and privacy. Privacy and confidentiality will be maintained at all  
25 levels by only consenting patients and caregivers in a private setting even when hospitalized at the time of enrollment. Patient and caregivers  
26 will be given separate smart phones with separate login information that does not contain any PHI. The login information copy will also be  
27 kept with the nurse coordinator in case the patients/caregivers forget them and needs to call the coordinator.

28 None of the devices has PHI stored in them and using the HIPAA-compliant servers, all data will be pushed onto the servers when entered. In  
29 case the smartphones are lost, misplaced or stolen, therefore there is no risk to PHI. Important to note is that there is no PHI stored on the any  
30 devices and therefore misplacing a device will not compromise patient data integrity. All data is pushed out to the device once login has been  
authenticated. First login is established after a two-factor authentication challenge is completed.

31 Once done, the patient is able to set a user and password for subsequent logins. All data resides on a HIPAA compliant Patient Buddy  
32 server which offers its own set of data security protections and backup. In the event a device is lost or stolen, no PHI data will be  
33 compromised. Our budget for PatientBuddy includes support for extra devices that will be made available to patients that lose or break a  
34 device with minimal disruption expected to the study and replaced in an unscheduled visit. Breaches in data security, although not expected  
35 given that no PHI resides on the phone, will be reported to the patients and caregivers within 24 hours of us receiving any such information  
36 from CITI. This will also be reported to the IRB and an urgent conference between the study team and CITI will occur to assess the root  
cause and prevent future episodes. All data will be de-identified for analysis.

37 They may feel anxious about completing the cognitive tests especially if they notice a decline. Since hepatic encephalopathy is a major reason  
38 for admissions, this cognitive testing tool is a critical tool for the study. Therefore If we find a participant is unwilling to use this app feature,  
39 they will be excluded.

40 2. Financial risks: since groups 2 and 3 will be in greater contact with their care team, they may be referred to  
41 their medical team for treatment or medication changes (for example), which may result in unanticipated costs  
42 for the participant. Although we will discuss these issues with our subjects at consent, we will also note being admitted to the hospital  
43 is a larger cost that may be avoided.  
44

45 35. **Where appropriate, discuss provisions for ensuring necessary medical, professional, or psychological intervention in the event of  
adverse events to the subjects:**

46 The process for addressing any significant subject reported medical issues through the buddy app is as follows:  
47 The Buddy App will be checked throughout the day by the study coordinator. When a subject or caregiver notifies the study coordinator  
48 that he/she is having problems or questions, the coordinator will provide answers and support within his/her scope of practice. However, if  
49 the issues are more complex and need a physician's oversite, he/she will contact the PI and/or the medical team for direction. The medical  
50 team may chose to call the subject/caregiver directly, or may give the coordinator instructions to give the subject/caregiver. The coordinator  
51 will then contact the subject/caregiver with this information (and will document the instructions) The coordinator will also follow-up later to  
52 check on the subject and determine if the issue is under control/resolved.

53 If the issues are more complicated and the medical team wishes to examine the subject or feels the subject needs an outpatient intervention  
54 such as a paracentesis, the coordinator will facilitate a clinic appointment with the medical team in clinic and will check on the patient/caregiver  
55 and update any changes in care and/or medications in the buddy app.

56 In regards to answering your question re. what the medical team will do, this will be tailored to the needs of the patient/subject and will be  
57 different for each patient. Our hepatology patients with cirrhosis have many clinical problems and are frequently followed in clinic for labs,  
ultrasounds, paracentesis, medication adjustments, etc.

58  
59 49. \* **Describe any potential for direct benefits to participants in this study:**

60 Patients with cirrhosis and their caregivers suffer from several issues that can lead to multiple readmissions. Most of these issues are

1 preventable by improving communications between patients/caregivers and the clinicians through intuitive mobile health applications.  
2 Therefore the use of Patient Buddy app and its streamlining using the pilot study is a critical step in empowering patients and caregivers in  
3 communicating with the team and preventing expensive and often unnecessary readmissions. Therefore this research is very useful for  
3 patients, caregivers, health care workers and potentially for society.

4 **5. \* Describe the scientific benefit or importance of the knowledge to be gained:**

5 Readmissions in decompensated cirrhosis are a significant unresolved burden that affects more than 1 million patients and caregivers  
6 throughout the US. Prior federally-funded research clearly shows preventable reasons for these readmissions that need to be disseminated  
7 to the clinicians, patients and caregivers. Utilizing the secure Patient Buddy App to serve as a portal of communication and education between  
8 patients/caregivers and clinicians will serve as a platform for future research focused on prevention of cirrhosis readmissions.

9  
10  
11  
12  
13  
14  
15  
16  
17  
18  
19  
20  
21  
22  
23  
24  
25  
26  
27  
28  
29  
30  
31  
32  
33  
34  
35  
36  
37  
38  
39  
40  
41  
42  
43  
44  
45  
46  
47  
48  
49  
50  
51  
52  
53  
54  
55  
56  
57  
58  
59  
60

1  
2  
3 Buddy App Protocol changes  
4  
5  
6

7 **Protocol Amendment 1**  
8

9 Changes to exclusion criteria: edit existing criteria to allow alcohol use within one month provided  
10 subject has not had alcoholic hepatitis within 1 month; allow subjects on hemodialysis  
11

12 Justification: To increase generalizability  
13

14 **Protocol Amendment 2**  
15

16 Due to COVID-19 related gap in enrollment, funding shortfalls, and low likelihood of us reaching the  
17 original study goals, a re-evaluation of the data was done to see if we could combine the two health-IT  
18 groups. Avoidable readmissions were similar across the 2 health IT groups and therefore, instead of 1:1:1  
19 randomization, this was changed to 1:1 randomization with a total of 464 subjects ( 232 patients and 232  
20 caregivers).  
21

22 Justification: reduced enrolment requiring combination of the groups.  
23

24  
25  
26  
27  
28  
29  
30  
31  
32  
33  
34  
35  
36  
37  
38  
39  
40  
41  
42  
43  
44  
45  
46  
47  
48  
49  
50  
51  
52  
53  
54  
55  
56  
57  
58  
59

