36 readmissions in patients with cirrhosis and their caregivers compared to standard of care.**

37  
38 As part of this specific aim, we will include 450 total cirrhotic patients and 450 caregivers (150 patients and 150 caregivers per center), who will  
39 be followed for 30 days post-discharge. The groups will be randomized 1:1:1 into a standard  
40 of care group, a group receiving health IT interventions who will receive PatientBuddy and EncephalApp Stroop with as-needed follow-up and  
41 another group that receives the same health IT interventions along with scheduled outpatient visits and calls within 30 days of discharge.  
42 Avoidable readmissions will be adjudged using a blinded adjudication committee and the differences between the three groups will be compared.  
43

44 The Health IT groups will be given iPhones loaded with the Patient Buddy app with caregiver and patient interfaces. They will be instructed  
45 extensively regarding the use of the App, which is preloaded with variables that associated with readmissions such as medications and  
46 adherence, issues with cognition and orientation and new symptoms. The patient and the caregiver will have separate devices linked to a device  
47 with the nurse coordinator through which daily communication will occur between patient/caregivers and the study team regarding previously  
48 identified risk factors associated with readmission. With this enhanced communication and educational value of the App, the study team will  
49 have greater access to events at patients' homes and the potential to prevent readmissions by intervening at that stage. The team will also  
50 engage the end-users (patients, caregivers and the nurse coordinator) by inquiring about their input in order to enhance the interface, user-  
51 friendliness and impact of the App. A detailed analysis of 30-day readmissions, including potential preventability with Patient Buddy will be  
52 performed. CITI will be responsible for establishing and monitoring the communication channels and implementation of the interfaces.  
53  
54  
55  
56  
57  
58  
59  
60

1 **Specific aim 2: To incorporate the opinion of key stakeholders (patients, caregivers and nurse coordinators) towards improving the**  
2 **Patient Buddy App in the prevention of readmission in cirrhosis**

3 The input of patients, caregivers and nurse coordinator and analysis of potential preventability of readmissions in specific aim 1 will be used  

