Training will be given to all patients and caregivers regarding

(a) cirrhosis (b) hepatic encephalopathy (c) ascites and low-sodium diet and (d) individual medication evaluation, using printed standardized patient information handouts from UptoDate. We will answer all questions raised by the patients and caregivers and the team will also individualize training based on the specific reason for admission.

We will then proceed with 1:1:1 site-specific randomization in blocks of 4 using a random number generator overseen by the statistician that will be communicated to the sites beforehand.

48

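### Amendment 2 merges the health-IT arms and changes allocation mid-trial without stating a two-group analysis; stratifying by allocation period is a cheap safeguard against a conditional bias (low severity)

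*Combined protocol and SAP*

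**What the plan says.** The randomisation paragraph of the protocol sets out three arms: "We will then proceed with 1:1:1 site-specific randomization in blocks of 4 using a random number generator overseen by the statistician". Specific Aim 1 gives the only comparison in the documents: "Avoidable readmissions will be adjudged using a blinded adjudication committee and the differences between the three groups will be compared". It names no test, model or stratification factor.

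Protocol Amendment 2 reports a COVID-19 enrolment gap, a funding shortfall and a re-evaluation of the data. It then says "Avoidable readmissions were similar across the 2 health IT groups and therefore, instead of 1:1:1" "randomization, this was changed to 1:1 randomization with a total of 464 subjects", that is, 232 patients and 232 caregivers. The reason given is "Justification: reduced enrolment requiring combination of the groups". It does not give the number randomised before the change, the two-group analysis that replaces the three-group one, or the power for 232 patients.

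Protocol Amendment 1, which is undated, widened eligibility. Alcohol use within one month is allowed provided the "subject has not had alcoholic hepatitis within 1 month; allow subjects on hemodialysis".

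The sample-size section assumes a "30-day readmission rate around 33% using current practice, and of which 20% were" avoidable, and for health-IT it chose to be cautious "and increase this relative avoidable readmission rate to 9"%.

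**The concern.** Under 1:1:1 the two health-IT arms, once merged, outnumber control two to one. After the change the ratio is one to one. Patients enrolled early are therefore over-represented in the health-IT group, and arm is associated with enrolment period even though each period is properly randomised.

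This does no harm if the risk of avoidable readmission is the same in both periods. If the risk differs, a comparison that ignores period mixes part of the time trend into the treatment effect. Rising risk makes health-IT look better than it is, and falling risk makes it look worse. Some two-group analysis now has to be chosen. With none written down, nothing ensures that it will respect the change in ratio.

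**Working it through.** **The plan's own figures.** A three-group chi-square test (2 df, alpha 0.05) at 20%, 9% and 9% needs 133 per arm for 80% power, close to the planned 135 per arm (405). Then 405 / 0.90 = 450, as stated. The 232 patients of Amendment 2 come with no assumptions, so there is nothing to reproduce.

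**Inputs.** N = 232 and the two ratios come from the documents. The number enrolled before the change and any shift in risk are not given; both are assumptions, shown as ranges. No treatment effect is assumed when bias and error are computed.

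**Bias formula.** Let s be the share of an arm that enrolled early. The expected crude difference (health-IT minus control) is (s_IT - s_C) x (early risk - late risk). With a fraction f enrolled early under 2:1 and the rest under 1:1, s_IT = 4f/(3+f) and s_C = 2f/(3-f). At f = 0.5 this is 0.571 - 0.400 = 0.171. The maximum is 0.172, near f = 0.51.

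**Reading 1: 2:1 before, 1:1 after.** The error is for a pooled two-proportion z-test, |z| > 1.96, by exact binomial enumeration.

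| Early patients | IT/control early | IT/control late | Gap in early share (points) | Bias for a 10-point shift (points) | Error, 10% to 20% | Error, 20% to 10% |
|---|---|---|---|---|---|---|
| 60 | 40/20 | 86/86 | 12.9 | 1.3 | 6.1% | 5.6% |
| 90 | 60/30 | 71/71 | 16.1 | 1.6 | 5.8% | 6.0% |
| 120 | 80/40 | 56/56 | 17.2 | 1.7 | 6.6% | 5.9% |
| 150 | 100/50 | 41/41 | 16.0 | 1.6 | 6.4% | 5.6% |
| 180 | 120/60 | 26/26 | 12.4 | 1.2 | 6.1% | 5.4% |

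- Over all splits from 60 to 180 in steps of 6, two-sided error is 5.3-6.9% for a 10-point shift, 4.8-5.9% for a 5-point shift and 4.5-5.4% for no shift.
- In the five tabulated splits, the affected tail for a 10-point shift is 3.9-5.7% (nominal 2.5%).
- Outside that range of splits the gap shrinks: 3.3 points with 12 early patients, 7.5 with 30 and 6.3 with 210.
- Stratified by period (Mantel-Haenszel), the error is 4.9-5.0% at risks of 10-20%.

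**If the planning rates are shares of the 33%.** Then 0.33 x 20% = 6.6% and 0.33 x 9% = 3.0%, a difference of 3.6 points. A shift between 3.3% and 6.6% gives 0.4-0.6 points of bias. Error is 4.7-6.1%, against 4.3-5.7% with no shift, so most of the spread is discreteness.

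**Reading 2: 1:1 means final totals of 116:116.** Later enrolment must then favour control. At 60 early patients the gap is (40 - 20)/116 = 17.2 points; at 150 it is (100 - 50)/116 = 43.1 points. A 10-point shift gives 1.7-4.3 points of bias and about 6-16% error.

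**Cost of stratifying with no shift.** The variance ratio is [T x C/(T + C)] / [sum over periods of t x c/n], where T, C are the arm totals and t, c, n the health-IT, control and total numbers in a period.

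- Reading 1: 1.021-1.029. Power for 20% vs 9% is 66.0-68.5% crude and 65.7-66.7% stratified. For 6.6% vs 3.0% it is 25-29% and 25-27%. The largest loss is about 2.7 points.
- Reading 2 costs more. At 60 early patients, 58 / (40x20/60 + 76x96/172) = 58/55.75 = 1.04. At 150, 58 / (100x50/150 + 16x66/82) = 58/46.21 = 1.26.

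**Group 2 versus group 3.** The 95% half-width at 9% risk is 1.96 x sqrt(2 x 0.09 x 0.91/n): 17.7 points at n = 20 per arm and 10.2 at n = 60.

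**The case against.** **No crude test is planned.** This stands. Amendment 2 is a few lines long, and its silence on stratification does not mean that an unstratified test was chosen. The supportable point is that no two-group analysis is stated. Nor is the contrast between the three-arm body text and the amendment itself an error: the amendment defines the current design, and the gap is that no stated analysis matches it.

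**The effect is small.** Under 2:1 then 1:1 this also stands. A 5-point shift barely moves the error, and visible inflation needs risk to double or halve. It is less secure under equal final totals, where the gap can reach 43 points.

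**The size rests on unknowns.** This stands too. The early count is not given. Exact 2:1 cannot be confirmed either, because blocks of 4 do not divide evenly among three arms.

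**A stronger reading is tempting:** that the COVID-19 gap and the wider eligibility changed the risk, so that the result is biased or favours health-IT. The documents do not support this. They report an interruption in enrolment, not a change in readmission risk. Amendment 1 is undated and may have applied to most patients in both periods. No rates by period are given.

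**Conclusion.** The point holds as a cheap improvement of low severity. The mid-trial change in ratio and the absence of a matching two-group analysis are plain in the text; the bias is conditional.

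If allocation is 2:1 then 1:1, an unstratified comparison absorbs up to about 17% of any shift in risk between periods. For a 10-point shift that is at most about 1.7 points, against a planned difference of 11 points (20% vs 9%). If 1:1 means equal final totals, the exposure is larger. With no shift it is zero, and neither a shift nor its direction is shown. A reader should not infer that the trial's error rate is in fact inflated.

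The figures assume that 232 is the whole-trial patient total and that the stated ratios were delivered exactly.

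Stratification deals only with a time trend. It does not address the merging of arms after a look at the outcome data, or the unstated power for 232 patients.

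**What to change.** Add to the analysis plan, before the results are examined:

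- The primary comparison is pooled health-IT versus standard of care, stratified by allocation period (before or after the change in ratio), using the Cochran-Mantel-Haenszel test with the Mantel-Haenszel risk difference and its 95% CI.
- The numbers randomised to each arm under each ratio are reported, with a statement of whether 1:1 refers to later allocation or to final totals.
- Group 2 versus group 3 is reported from patients randomised under 1:1:1 only, with its 95% CI. This keeps Aim 1's question about scheduled visits and shows how precise the finding of similarity is.

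This is wording only, with no new data. Under 2:1 then 1:1, and with no shift, it costs about 2-3% in variance and at most about 2.7 points of power. Under equal final totals the variance cost is higher, about 4-26% at 60-150 early patients, but the bias it guards against is also larger.
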